ASSOCIATION BETWEEN PROGRESSION FREE SURVIVAL AND OVERALL SURVIVAL IN WOMEN RECEIVING FIRST-LINE TREATMENT FOR METASTATIC BREAST CANCER: EVIDENCE FROM THE ESME REAL-WORLD DATABASE

IB-2017DATECAN-ESME
NCT03676257
Version n°1.0 05/01/2020

Coordinating Investigator
[name]

Scientific responsive
[name]

Clinical Research Unit

[name], PhD
Head of the Unit

Institut Bergonié, Bordeaux

SPONSOR

INSTITUT BERGONIÉ

Title of the study	ASSOCIATION BETWEEN PROGRESSION FREE SURVIVAL AND OVERALL SURVIVAL IN WOMEN RECEIVING FIRST-LINE TREATMENT FOR METASTATIC BREAST CANCER: EVIDENCE FROM THE ESME REAL-WORLD DATABASE
Abbreviation of the trial	DATECAN-ESME
Sponsor Identification	Institut Bergonié, Comprehensive Cancer, Bordeaux
Coordinating Investigator	[name]
Scientific responsive	[name]
Number of investigational sites planned	18
Number of patients	20033
Duration of the study	Retrospective study
Medical conditions	Metastatic breast cancer
Rationale of the study	
Overall survival (OS) is the gold standard endpoint to assess treatment efficacy in cancer clinical trials.
 
In metastatic breast cancer (mBC), progression-free survival (PFS) is commonly used as an intermediate endpoint.
 
Evidence remains scarce regarding the degree of association between PFS and OS. Our study aimed to describe the individual-level association between real-world PFS (rwPFS) and OS according to first-line treatment in female patients with mBC managed in real-world setting for each BC subtype (defined by status for both hormone-receptor [HR] expression and HER2 protein expression/gene amplification).

Objectives	
To estimate rwPFS, OS and association between rwPFS and OS according to first-line treatment in female patients with mBC managed in real-world setting for each BC subtype (defined by status for both hormone-receptor [HR] expression and HER2 protein expression/gene amplification).

Study design	
Retrospective study
 
The Epidemio-Strategy and Medical Economic (ESME) Research Program is a French academic initiative supporting the centralization of structured and non-structured data documented in the electronic health records (EHR) (clinical notes, pathology reports and radiology reports) of patients treated for malignant conditions in a unique secured web-based data platform available for researchers.
 
The ESME mBC data platform is an EHR-derived database that gathers exhaustive data on consecutive patients who initiated a L1 treatment for mBC between 01 January 2008 and 31 December 2017 in one of 18 French Comprehensive Cancer Centers (clinicaltrials.gov; NCT 03,275,311). Patients who only receive surgery of a breast-related metastatic lesion are not eligible for selection into the ESME mBC database

Randomization and Treatment groups	Not applicable
Eligibility criteria	All female patients older than 18 years diagnosed with mBC (de novo disease or first metastatic recurrence) between January 1, 2008, and December 31, 2017, and who received a L1 systemic treatment such as chemotherapy, endocrine therapy or targeted

	
therapy, whatever the sequence (monotherapy or combination of therapies using distinct mechanisms of actions, i.e., polytherapy).
 
A treatment line is defined as all anti-cancer treatments received in the absence of tumor progression.
 
Patients without informative data for tumor subtype are excluded (e.g., status for both HR expression and HER2 expression/gene amplification).
 
Patients receiving radiation therapy or anti-resorptive drugs (e.g., bisphosphonates, denosumab) as unique treatment are not considered in the analysis.
 
Patients are excluded if a second breast cancer was diagnosed before the onset of metastatic disease in order to limit potential inconsistencies between both breast cancer tumor subtypes and the metastases.

Treatment schedule and route of administration	This is a retrospective study, based on clinical records.
Endpoints	
rwPFS : time from initial diagnosis of mBC to the date of disease progression (regional recurrence, progression, appearance/occurrence of metastases and distant recurrence) or death (any cause), whichever came first.
 
OS : time from diagnosis of mBC to the date of death from any cause.

Statistical analysis plan	
This is a retrospective study, based on clinical records.
 
Sample size : On April 14, 2020, the ESME mBC database included a total of 23,697 mBC subjects. Of those, 20,033 satisfy the eligibility criteria for our study population
 
Statistical Analysis Plan (SAP)
 
Baseline characteristics will be summarized using frequency and percentage for qualitative variables. Median and inter-quartile range will be reported for quantitative variables. We will report frequencies and proportions for variables with missing or not documented information. No statistical test will be performed for the descriptive analyses.
 
Median follow-up will be estimated using the reverse Kaplan–Meier Method. Survival data will be estimated using Kaplan–Meier method and we will report median survival times with their respective 95% confidence interval (95%CI). Data for patients without the events of interest will be censored at the date of last contact recorded in the database.
 
We will estimate the individual-level association between rwPFS and OS using a Spearman rank correlation coefficient expressed as a value between 0 (no association) and 1 (perfect association) with 95% CI. Copula models allow one to jointly model two time-to-event variables. We will use a reviewed copula-based approach that introduced an iterative multiple imputation method for the estimation of the correlation coefficient. The strength of the rwPFS/OS association will be ranged according to the estimated correlation coefficient as follows: 0–0.19 is considered as very weak, 0.2–0.39 as weak, 0.40–0.59 as moderate, 0.6–0.79 as strong, and 0.8–1 as very strong correlation. We will estimate and report individual rwPFS/OS associations according to mBC subtype and first-line mBC treatment.
 
Data will be analyzed using R software (v 3.6).

IDMC	Not applicable

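### rwPFS runs from mBC diagnosis and does not require progression to follow the start of first-line treatment, so pre-treatment events can count in first-line treatment cells and bias rho in either direction

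*Combined protocol and SAP*

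**What the plan says.** The protocol and SAP are one document in synopsis form. Four of its rows bear on this point.

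- **Endpoints.** The rwPFS clock starts at diagnosis and stops at the first listed event: "time from initial diagnosis of mBC to the date of disease progression (regional recurrence, progression, appearance/occurrence of metastases and distant recurrence"), or death if that is earlier. OS has the same origin: "OS : time from diagnosis of mBC to the date of death from any cause".
- **Objectives.** The aim is "To estimate rwPFS, OS and association between rwPFS and OS according to first-line treatment", within each subtype. The Statistical analysis plan row repeats that the correlations are reported by subtype and first-line treatment.
- **Eligibility criteria.** A woman must be one "who received a L1 systemic treatment such as chemotherapy, endocrine therapy or targeted" therapy. No maximum interval from diagnosis to L1 start is set. A line is defined thus: "A treatment line is defined as all anti-cancer treatments received in the absence of tumor progression". Local or bone-directed treatment excludes only when nothing else is given: "Patients receiving radiation therapy or anti-resorptive drugs (e.g., bisphosphonates, denosumab) as unique treatment are not considered in the analysis".
- **Study design.** Women whose only treatment is surgery of a metastatic lesion are not in the database. The database selects on the date L1 was initiated.

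No row gives a baseline-staging window or says what to do with a progression dated before L1 start.

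**The concern.** The event window opens at diagnosis, while the grouping variable is a treatment that starts later. A progression in between is dated before the exposure by which it is tabulated, so it carries no information about outcome on that treatment. It still enters that treatment's rwPFS median and its rwPFS/OS correlation.

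Two kinds of event could fall in the interval. One is true progression before systemic treatment, for example after local treatment of a lesion. The other is a further metastatic site recorded while staging is being completed. Every woman has metastases at time zero, and the event list includes new metastases without a baseline window.

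What is at stake is the study's main output. Rho per cell is classed into bands (moderate 0.40 to 0.59, strong 0.6 to 0.79). A bias that varies between cells with staging practice and early use of local treatment would distort comparisons between them and could move a cell near a boundary.

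**Working it through.** **Step 1: the rule.** Let D be diagnosis, L the start of L1, P the first recorded progression and X death. The plan sets rwPFS = min(P, X) − D. Eligibility requires L1 to have been received, so X cannot precede L. Nothing requires P > L. If D < P < L, the plan's rwPFS is P − D with an event, and the woman is placed in the cell of the treatment started at L.

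**Step 2: direction for rwPFS.** rwPFS is a minimum, so adding an earlier event can only shorten it relative to the same origin without that event. The diagnosis origin separately adds L − D to both endpoints, which lengthens them.

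**Step 3: direction and size for rho.** The plan states no expected rho, median, diagnosis-to-L1 interval or early-event rate, so there is no planned figure to reproduce. The 20,033 patients are a database count. I simulated 400,000 women per scenario, without censoring, using plain Spearman. Every input below is an assumption.

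*Model A.* Shared gamma frailty with variance 0.3; exponential time to progression, death without progression (median 120 months) and post-progression survival. In a randomly chosen share f, rwPFS becomes the smaller of its true value and a uniform 0 to 1 month time.

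| Median progression / post-progression (months) | f = 0% | 2% | 5% | 10% |
|---|---|---|---|---|
| 9 / 18: rho | 0.58 | 0.56 | 0.53 | 0.48 |
| 9 / 18: median rwPFS (months) | 9.3 | 9.0 | 8.5 | 7.7 |
| 5 / 8: rho | 0.63 | – | 0.58 | – |
| 12 / 28: rho | 0.54 | – | 0.49 | – |

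The result changes when early events are linked to prognosis. With probability proportional to frailty, the 5/8 cell falls only to 0.60 at 5%. With early events strongly concentrated in women with short OS, the 9/18 cell rises from 0.58 to 0.61 at 10%.

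*Model B.* Log-normal frailty (SD 0.5); median 9 months from L1 to progression and 20 months afterwards; exponential diagnosis-to-L1 gap with mean 1 month, added to both endpoints. A share f has its rwPFS event moved to a random point in the gap. These women are chosen either at random or as the lowest f on log OS plus normal noise (SD 0.5).

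| f | Random: rho (median, months) | Short OS: rho (median, months) |
|---|---|---|
| 0% | 0.548 (9.74) | 0.548 (9.74) |
| 1% | 0.537 (9.61) | 0.550 (9.74) |
| 5% | 0.496 (9.04) | 0.572 (9.71) |
| 10% | 0.447 (8.31) | 0.604 (9.55) |

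At 10% the change in rho is 0.447 − 0.548 = −0.101 or 0.604 − 0.548 = +0.056. The signs are the same with frailty SD 0 (0.437 to 0.356 or 0.510) and SD 1.0 (0.700 to 0.574 or 0.732).

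**Step 4: the origin alone.** In Model B without early events, rho is 0.546 from L1 start and 0.548 from diagnosis. Median rwPFS is 8.68 against 9.74 months, a difference of 1.06 months, about the mean gap. With a gap of this length, moving the origin hardly changes rho. What matters for rho is whether pre-L1 events count.

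**The case against.** The strongest objection is that the plan may produce few such events or none.

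- **Staging lesions.** The list is a parenthesis explaining disease progression. A careful abstractor need not treat lesions found during completion staging as progression, and the database's coding rules are not shown. A reader might infer that staging findings definitely become events. The documents support this only as a literal reading that nothing in the plan excludes.
- **Local treatment first.** The exclusions let in a woman who has local treatment, progresses and then starts systemic therapy. But if local treatment counts as anti-cancer treatment, the line definition says that her progression closed that line. Her later drug is then not L1 and she may fail inclusion. A reader might infer that she is clearly eligible; the text does not settle it.
- **Direction of rho.** A reader might infer that rho is always lowered. That holds for events unrelated to prognosis. It does not hold generally, because true early progression may be concentrated in women who die early.
- **Size.** The share of early events is unknown, the plan's estimator is copula-based with iterative multiple imputation rather than plain Spearman, and most simulated cells stay within their band at 5%.

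All four points stand as limits on what can be claimed. None removes the defect: a recorded progression dated before L1 counts under the rule as written, and the plan would not show how often this happens.

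**Conclusion.** The point holds as a flaw in the endpoint rule. Followed as written, it assigns any progression between diagnosis and L1 start to the cell of a treatment not yet begun. This is more than missing detail, because the stated origin and event rule themselves give that result.

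Only the shortening of rwPFS is certain in direction, and only against the same origin without those events. Rho is biased down by events unrelated to prognosis (0.58 to 0.53 at an assumed 5%, 0.48 at 10%) and up by events strongly concentrated in women with short OS (0.58 to 0.61 at 10%). A band change is possible either way: 0.63 to 0.58 in the 5/8 cell at 5% random events, or 0.548 to 0.604 in Model B at 10% concentrated events. It needs a cell near a boundary or a large share of early events.

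The sizes rest on assumed survival models, no censoring and an assumed 2% to 10% share. The documents support neither a certain downward bias in rho nor any particular frequency. The rule should be changed, and the events counted, before results by first-line treatment are interpreted.

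**What to change.** Amend the Endpoints and Statistical analysis plan rows as follows.

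1. Measure both rwPFS and OS from the start of L1 systemic treatment, for all women. Shifting the origin only for affected women, or only for rwPFS, would mix clocks within a cell or between the two correlated endpoints.
2. Count a progression, recurrence or new metastasis as an rwPFS event only if dated after L1 start. Lesions documented up to L1 start are baseline disease. The new origin needs this explicit rule for pre-L1 events.
3. Report the number of pre-L1 events per subtype and treatment cell.
4. Keep the diagnosis-origin analysis as a sensitivity analysis.
5. Reconcile the treatment-line definition with the eligibility rule for women who progress after local treatment and before systemic treatment, so that their inclusion is settled in the text.

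The cost is small: revised wording and a date comparison in existing data. The main analysis would have slightly fewer rwPFS events, and its survival times would no longer run from diagnosis. It would also rely on recorded L1 start dates. The database's selection on L1 initiation suggests that these are held, but the plan should confirm it.

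### Does labelling the strength of the rwPFS/OS association from the point estimate alone make the planned conclusions overprecise?

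*Combined protocol and SAP*

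**What the plan says.** The statistical analysis plan estimates the individual-level association as a "Spearman rank correlation coefficient expressed as a value between 0 (no association) and 1 (perfect association) with 95% CI". It then gives the verbal scale: "The strength of the rwPFS/OS association will be ranged according to the estimated correlation coefficient as follows", with cut-points at 0.2, 0.4, 0.6 and 0.8. The upper bands read "0.40–0.59 as moderate, 0.6–0.79 as strong, and 0.8–1 as very strong correlation". The scale applies to a set of cells: "We will estimate and report individual rwPFS/OS associations according to mBC subtype and first-line mBC treatment". This matches the Objectives entry of the synopsis: "To estimate rwPFS, OS and association between rwPFS and OS according to first-line treatment", for each breast cancer subtype.

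Estimation is by copula with iterative multiple imputation; no variance formula for the interval is given. The sample size is a database count ("Of those, 20,033 satisfy the eligibility criteria for our study population"). The documents give no list of treatment categories, no cell sizes, no minimum cell size, and no method for comparing coefficients between cells.

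**The concern.** The adjective is the only interpretive rule the plan offers for its main result, and the interval plays no part in choosing it. In a small cell, an estimate called *moderate* may have an interval running from *weak* to *strong*. Close to a cut-point, even a large cell can land on either side by chance. The results will probably be read as a list of labels by subtype and treatment, so a reader could take *moderate* in one cell and *strong* in the next as a real difference. The stake would be a false impression that PFS tracks OS better under one treatment, or in one subtype, than another. The rationale says that evidence on this association is scarce, so such an impression could carry weight.

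**Working it through.** **Figures in the plan.** There is no precision or power calculation to reproduce. The 20,033 patients are a count out of 23,697 (20,033 / 23,697 = 84.5%; 3,664 not eligible).

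**Inputs.** From the plan: cut-points 0.2, 0.4, 0.6, 0.8 and a 95% interval. Assumed: complete data, cell size n and true rho. The interval is approximated on the Fisher scale as tanh(atanh(r) ± 1.96 × SE), with SE = sqrt((1 + r²/2)/(n − 3)). The planned copula and imputation interval may differ, and censoring would tend to widen it.

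**Step 1: can an interval span more than one band? Yes.**
- r = 0.50, n = 100: SE = sqrt(1.125/97) = 0.108; interval 0.33 to 0.64, *weak* to *strong*.
- r = 0.50, n = 500: SE = sqrt(1.125/497) = 0.048; interval 0.43 to 0.57, *moderate* only.
- r = 0.60, n = 5,000: SE = sqrt(1.18/4,997) = 0.0154; interval 0.58 to 0.62, *moderate* to *strong*.

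The smallest n that keeps a mid-band estimate's interval inside one band is 356 at 0.30, 277 at 0.50 and 161 at 0.70.

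These are two different situations. At n = 100 the label really is finer than the data. At 0.60 with n = 5,000 the interval is about 0.04 wide and the band about 0.2 wide, so the label is *coarser* than the data. That is the boundary effect of any categorical scale, not false precision.

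**Step 2: how often do two cells with the same true rho get different labels, and do the planned intervals show it?** One million simulated pairs per n, rho uniform on 0.3 to 0.8:

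| n per cell | labels differ | of those, the two 95% intervals overlap | median gap between estimates |
|---|---|---|---|
| 100 | 40% | 99% | 0.12 |
| 200 | 29% | 98% | 0.09 |
| 500 | 18% | 98% | 0.055 |
| 1,000 | 13% | 98% | 0.038 |
| 5,000 | 6% | 98% | 0.02 |

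At n = 500, different labels *and* separated intervals occur in about 0.18 × 0.02 = 0.4% of same-rho pairs. Overlap is a lenient criterion, but it is the comparison a reader can make from the planned output. Label errors of two or more bands occur in 0.2% of draws at n = 100 and almost never from n = 200.

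**Step 3: a worked pair.** Estimates of 0.57 and 0.63 with n = 500 each are labelled *moderate* and *strong*. Their intervals are 0.503 to 0.631 and 0.568 to 0.685, which overlap plainly. Combining them (MOVER) gives a difference of 0.06 with limits
- 0.06 − sqrt((0.63 − 0.568)² + (0.631 − 0.57)²) = −0.03
- 0.06 + sqrt((0.685 − 0.63)² + (0.57 − 0.503)²) = 0.15

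The planned intervals are enough to see that the labels do not support a contrast.

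**Step 4: how far does the rate depend on assumptions?** The ranges 0.2–0.9, 0.4–0.7 and 0.5–0.8 give 35 to 41% at n = 100 and 11 to 14% at n = 1,000, but all of them contain the 0.6 cut-point. With rho uniform on 0.65 to 0.75 the rate is 21% at n = 100, 1.2% at n = 500 and 0.1% at n = 1,000. With rho exactly 0.60 it is about 50% at any of these sizes. The documents do not say where this study lies.

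**Step 5: does anything in the plan rest on the label?** The rationale and objective speak of describing and estimating. No sentence plans to rank cells, test a difference in correlation, or act on a band.

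**The case for a change.** The best case for the concern is that readers remember adjectives, not intervals. The bands are the plan's only rule for interpreting its main result, labels from different cells will be compared, and the total of 20,033 does not guarantee precision within each subtype-by-treatment cell. Shifts between adjacent bands, such as *moderate* to *strong*, are the ones that would change a conclusion. Two added sentences would be cheap: one naming the bands each interval covers, one barring contrasts based on labels alone.

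The factual part stands. The label does ignore the interval, cell sizes are unknown, and in cells of 100 to 200 the adjective alone says more than the data can.

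The step to a defect does not. The first sentence would only restate a reported number more crudely: 0.58 to 0.62 would become *moderate to strong*, which verbally covers 0.40 to 0.79, a span of 0.39 against 0.04, or roughly ten times the real interval. Under the Step 2 model such wording would attach to 63% of cells at n = 500, 44% at n = 1,000 and 20% at n = 5,000. The second would forbid a claim the plan never makes. If a later report did claim a difference between cells on labels alone, that would be a fault of the report.

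**Conclusion.** The concern does not hold as an error in the plan. The point-estimate label is a descriptive convention, applied the same way in every cell and printed with a 95% interval. Followed as written, the plan gives the same coefficients and intervals whichever adjective is attached, and no test or decision uses the adjective. Chance differences in label between equal cells can be common (6 to 40% for 5,000 down to 100 per cell, with rho uniform on 0.3 to 0.8), but in about 98 to 99% of those cases the planned intervals overlap.

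These rates assume complete data, a Fisher-type interval, equal cell sizes and an assumed spread of true correlations; none of these can be checked from the documents, and the real rate could be near zero or substantial. The conclusion does not depend on the rate. It rests on two features of the text: the interval is planned for every coefficient, and no comparison between cells is planned.
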